11.5. Decision points

As specified in section 9.7., interim analyses of each patient's baseline data will be performed after the first night of the first visit. This will help establish a familiarity with each participant's sleep stage duration and EEG morphology, their maximum sleep depth as well as the presence of pathological sleep features. Based on this knowledge, decisions on the timing of the stimulation during the second night will be made by the PI and sleep scientist team, as well as basic assumptions on the desired effects. Following the first visit, further interim analyses will determine to what degree these assumptions were correct, so that stimulation patterns can be explored further during the second visit.

11.6. Stopping rules

As a basic science study, this study will finish at the point at which the target sample size has been recorded.

11.7. The Level of Statistical Significance

Statistics will use standard conventions for reporting of significance, including effect size, and multiple testing statistics for experimental effects.

11.8. Procedure for Accounting for Missing, Unused, and Spurious Data.

All data will be pre-processed and screened for gross abnormalities/poor data quality. In the case where experimental conditions prohibited sufficient quality recordings to be made then all (or a subsection) of a participant's data will be excluded from the study.

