6. OBJECTIVES AND OUTCOME MEASURES

Objectives	Outcome Measures	Timepoint(s) of outcome measure
Primary Objectives		
Feasibility of study	Ability to recruit planned participant number and carry out scheduled experiments in reproducible fashion	
 Analyses post-study completion Some evidence during interim analyses per group
Effect of stimulation on sleep stages	EEG changes (frequency changes, changes in EEG patterns and sleep structure)	
 During stimulation Post-stimulation at specific sleep stages

Secondary Objectives
 
Effect of stimulation on sleep inertia and vigilance & performance during the day
 
Controlling sleep depth and sleep-wake transitions
	
Performance on short and long test battery (see section 9.6.3)
 
Assessment of effect on latency to sleep onset and REM sleep, number of sleep cycles, duration of sleep stages, number of awakenings per night, sleep efficiency
	
 Upon awakening (post-baseline night and post-intervention) During the day (post-baseline and intervention) During intervention nights

Tertiary Objectives
 
Effect of stimulation on other measures of arousal
	
Effect on autonomic measures such as heart-rate variability and blood pressure, as well as salivary cortisol levels
	
 Overnight measurements Salivary cortisol levels measured upon awakening each day (6am).

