9.5. Blinding and code-breaking

There will be no blinding in the study and therefore no code-breaking procedure is required.

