11.3. Sample Size Determination

This is a feasibility study into recruiting and conducting the study procedures in patient populations. Given the exploratory and novel nature of this study, effect sizes are as of now, unknown. We are collecting from different groups bearing in mind that a minimum n=3 is required for the most rudimentary statistics based on patient number. We therefore expect 15 patients to be the lowest bound for 5 different DBS electrode locations. There will be multiple comparable stimulation epochs per patient, across three nights (second night of first visit and both nights of second visit). The number of sleep stages and cycles per night will vary between participants, with an added unknown being the effect of the disease state on sleep. However, this within- and across-subject comparison will boost statistical power. Further support that an N-of-1 trial design can be used for closed-loop DBS research and provide individualized, precision data to inform device development, was published recently (Stevens and Gilbert 2020).

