11.4. Analysis populations

All data collected from participants who have completed the full study will be included in the analysis.

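### Sections 11.8 and 11.4, read literally, remove failed recording sessions from a study whose primary outcome includes whether the scheduled sessions can be carried out, so feasibility would be overstated.

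*Combined protocol and SAP*

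**What the plan says.** Section 11.8 (missing, unused and spurious data) has all data screened for quality during pre-processing. Its exclusion rule starts "In the case where experimental conditions prohibited sufficient quality recordings to be made then all (or a subsection" and concludes that this portion "of a participant's data will be excluded from the study". It gives no quality threshold, no criterion for choosing between removing everything and removing a part, and no requirement to report what was removed.

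Section 11.4 defines the only analysis population: "All data collected from participants who have completed the full study will be included in the analysis".

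Section 6 lists two primary objectives. The outcome for the first, feasibility, is "Ability to recruit planned participant number and carry out scheduled experiments in reproducible fashion". The second concerns the effect of stimulation on the EEG and sleep stages.

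Section 11.3 says that "a minimum n=3 is required for the most rudimentary statistics based on patient number" and continues "We therefore expect 15 patients to be the lowest bound for 5 different DBS electrode locations".

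Section 11.1 states that there is no separate SAP, and section 12 that there is no separate data management document. These sections are therefore the whole plan on this point.

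**The concern.** In many trials, dropping unusable signal is routine cleaning. Here, obtaining the recording is part of what is being tested. If a night in the monitoring unit yields no usable polysomnography, that scheduled experiment was not carried out, and this is a result. Section 11.8 treats it as data to be removed, and it says removed from the study, not from one analysis. Section 11.4 does the same for anyone who leaves before the second visit ends. No section defines a feasibility denominator or says that excluded or incomplete sessions count as not completed.

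The stake is the headline conclusion. A feasibility study that reports only the sessions that worked will look feasible whatever happened, and its result may then be used to plan further work.

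There is a second cost. Removing a whole participant when only part of the recording is bad discards valid data. The planned groups are too small to absorb that.

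**Working it through.** **The plan's own figure.** Section 11.3: 3 participants per location × 5 locations = 15. This reproduces. The plan gives no expected failure rate, so every failure count below is an assumption.

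**The rules followed literally.** Let n be the number enrolled and f the number whose recordings fail or who do not complete.

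- Failures counted: completion = (n − f)/n.
- Failures removed under 11.8 and 11.4: completion = (n − f)/(n − f) = 100% for any f below n.

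The second quantity carries no information about feasibility.

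**Size.** Intervals are exact (Clopper-Pearson) 95%. When every participant counted is a success, the lower limit is 0.025^(1/m), with m the number counted.

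Assumed 20 enrolled, 5 excluded:

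- counted: 15/20 = 75% (51 to 91%)
- removed: 15/15 = 100%, lower limit 0.025^(1/15) = 78%

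Assumed 15 enrolled, with 1, 3 or 5 failures:

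| f | counted | removed |
|---|---|---|
| 1 | 14/15 = 93% (68 to 100%) | 14/14 = 100% (77 to 100%) |
| 3 | 12/15 = 80% (52 to 96%) | 12/12 = 100% (74 to 100%) |
| 5 | 10/15 = 67% (38 to 88%) | 10/10 = 100% (69 to 100%) |

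The point estimate is overstated by 7, 20 or 33 percentage points.

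**Effect on the minimum per target.** With exactly 3 participants per target, one whole-participant exclusion takes that target below the plan's minimum. Section 9.10 provides, under conditions, for replacing withdrawn participants. It does not mention participants excluded for data quality. If each participant is excluded independently with probability q and none is replaced:

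- a given target falls below 3 with probability 1 − (1 − q)^3
- at least one of the five does so with probability 1 − (1 − q)^15

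| assumed q | given target | at least one target |
|---|---|---|
| 5% | 14% | 54% |
| 10% | 27% | 79% |
| 20% | 49% | 96% |

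**The case against.** The best defence is that section 11.8 is a signal-quality rule and was never meant to govern feasibility. It does not forbid counting failed sessions. Section 9.4 has enrolments recorded, section 9.10 puts withdrawals and their reasons in the CRF, and section 14 has deviations documented, so much of what is needed for a count will exist. The plan also defines no completion rate, so the percentages above concern a statistic it does not name. All of this is fair, and removing unusable signal from the EEG analyses is reasonable. It does not answer the point: the text says the data leave the study, the only analysis population is completers, and nothing says that the recorded failures will be reported against the primary outcome.

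A reader might go further and infer that recordings fail mainly under stimulation, so that the rule is differential by design. The documents do not support that. The term experimental conditions is undefined and the screen covers all data. Section 9.7 allows the baseline night to be recorded with usual stimulation on or off. In both Appendix A examples, Night 1 is on standard stimulation throughout, while most sleep stages on Night 2 are off. Loss related to stimulation is possible: low frequency is 2 to 40 Hz in section 7 (2 to 30 Hz in Appendix A), which overlaps the 0.25 to 32 Hz band of the spectral outcome. But neither its occurrence nor its direction is stated.

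A reader might also infer that exclusions will be made with the results in view. Section 9.5 says "There will be no blinding in the study", so the condition may be known. Section 11.8 places the screen in pre-processing, and no section says that outcomes are known when quality is judged.

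Nor does the plan say that one bad segment removes a whole participant. It allows partial exclusion and gives no criterion for choosing.

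**Conclusion.** The point holds as an overstatement of feasibility. Two stated rules, applied as written, remove failed or incomplete sessions from an outcome of which they are a part. They are only a part of it, since the outcome also covers recruitment. On the assumed counts the result moves from 75% to 100%; with 15 enrolled the gap runs from 7 points for one failure to 33 for five. These sizes depend on the assumed failures and on feasibility being summarised as a completion proportion, which the plan does not specify. The direction depends on neither the chosen counts nor the cause of failure: removing any failure can only raise the proportion. Bias between stimulation conditions is a possibility to monitor, not a finding. The change should be made before analysis.

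**What to change.** Amend sections 11.4 and 11.8 together, because changing 11.8 alone leaves the completers-only restriction in place.

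- **(a) Feasibility.** Every consented participant and every scheduled night stays in the feasibility outcome. An unusable or missing recording counts as not completed.
- **(b) Signal analyses.** The 11.8 exclusion applies only to the sleep and EEG analyses, at the smallest affected unit (epoch or night). A participant is left out of a contrast only when the data that contrast needs are unusable. A lost baseline night is the main case, because section 9.7 makes it the reference for the rest of the protocol.
- **(c) Reporting.** Exclusions are tabulated by night and stimulation condition, so that any imbalance can be seen.

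Having the quality screen done by someone unaware of the condition would help. However, the study team scores sleep in real time while overseeing stimulation, so this may need a separate scorer. It is not essential to the correction.

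The cost is a few sentences, one extra table, and a feasibility figure that may be less favourable.

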11.9. Procedures for Reporting any Deviation(s) from the Original Statistical Plan

Should a deviation from the original statistical plan imply a deviation from the pre-specified recruitment and testing protocol, the Funder and IRB members will be contacted by the Chief Investigator and the Study Steering Committee. No such deviation will be carried out without prior approval from these parties.

12. DATA MANAGEMENT

The plan for the data management of the study are outlined below. There is not a separate Data Management document in use for the study.

12.1. Source Data

Source documents are where data are first recorded, and from which participants' CRF data are obtained. These include, but are not limited to, hospital records (from which medical history and previous and concurrent medication may be summarized into the CRF), clinical and office charts, laboratory and pharmacy records, diaries, microfiches, radiographs, and correspondence.

CRF entries will be considered source data if the CRF is the site of the original recording (e.g. there is no other written or electronic record of data). All documents will be stored safely in confidential conditions. On all study-specific documents, other than the signed consent, the participant will be referred to by the study participant number/code, not by name.

12.2. Access to Data

Direct access will be granted to authorised representatives from the Sponsor and host institution for monitoring and/or audit of the study to ensure compliance with regulations. Reports and anonymized data may also be shared with named collaborators ([name], PhD Oxford UK and Assistant [name] [name], University of California, San Francisco).

The USAMRDC ORP HRPO conducts site visits as part of its responsibility for compliance oversight (as also stated in other relevant sections). Accurate and complete study records will be maintained and made available to representatives of the USAMRDC as a part of their responsibility to protect human subjects in research. Research records will be stored in a confidential manner so as to protect the confidentiality of subject information.

12.3. Data Recording and Record Keeping

A unique code will be assigned to each patient, which will consist of group, random number generator sequence, and number of participants during the recruitment process. A side file (Excel) will be created containing patient-specific data and code breakdown –it will be stored in lab premises, on a research computer with backup copy on a password-protected server.

Anonymized data may be stored in encrypted devices and password-protected laptops for analysis in other collaborating units.

Data will be retained beyond completion of the study until thoroughly analyzed as per objectives, We may also share encrypted and anonymized data with collaborating groups internationally.

The results of analysis that pertains to the data previously collected from patients with investigational RC+S under FDA-IDE G180224 will be included as part of the FDA reporting.

13. QUALITY ASSURANCE PROCEDURES

The study may be monitored, or audited in accordance with the current approved protocol, GCP, relevant regulations and standard operating procedures.

13.1. Risk assessment

A risk assessment and monitoring plan will be prepared before the study opens and will be reviewed as necessary over the course of the study to reflect significant changes to the protocol or outcomes of monitoring activities.

13.2. Study monitoring

Regular monitoring will be performed by an Independent Study Monitor, in addition to IRB requirements. The Study Monitor will not be a clinical research associate for the study and will be based in an independent institution –however they will share a relevant clinical background and role to the Principal Investigator (Consultant Neurologist) to ensure optimal ability of risk assessment. Data will be evaluated for compliance with the protocol and accuracy in relation to source documents as these are defined in the study specific Monitoring Plan. Following written standard operating procedures, the monitors will verify that the clinical study is conducted, and data are generated, documented and reported in compliance with the protocol, GCP and the applicable regulatory requirements.

The USAMRDC ORP HRPO also conducts random audits at the time of continuing review. Additional information and documentation may be requested at that time. The USAMRDC ORP HRPO also conducts site visits as part of its responsibility for compliance

oversight. Accurate and complete study records must be maintained and made available to representatives of the USAMRDC as a part of their responsibility to protect human subjects in research. Research records reviewed will be stored in a confidential manner so as to protect the confidentiality of subject information.

The final study report, including any acknowledgement documentation and supporting documents, must be submitted to the HRPO when available.

13.3. Study Committees

The USAMRDC ORP HRPO is responsible for conducting the following activities:

- Principal advisor to the Command for human subjects protection.
- Develop and implement human subjects protection policies & regulations.
- Maintain the USAMRDC Volunteer Registry Management System.
- Review and approve intramural and extramural human subjects protocols.
- Conduct human subjects protection site visits.

In that context (and explicitly stated as a requirement by the Funder), it is required that there is an annual IRB report with regards to the study. To facilitate this purpose, as well as ensure that the study runs smoothly across sites and collaborations, a Study Steering Committee (Profs [name], [name] and [name]) will meet at regular intervals to discuss progress and troubleshoot any issues.

14. PROTOCOL DEVIATIONS

A study related deviation is a departure from the ethically approved study protocol or other study document or process (e.g. consent process or administration of study intervention) or from Good Clinical Practice (GCP) or any applicable regulatory requirements. Any deviations from the protocol will be documented in a protocol deviation form and filed in the study master file. In case of non-compliance, details of the incident will be escalated to the central PI team and an assessment of whether it may be a potential Serious Breach will follow, as outlined in the relevant study SoP.

Substantive modifications to the research protocol and any modifications that could potentially increase risk to subjects must be submitted to the HRPO for approval prior to implementation, as per requirements of the Funder. The USAMRDC ORP HRPO defines a substantive modification as a change in Principal Investigator, change or addition of an institution, elimination or alteration of the consent process, change to the study population that has regulatory implications (e.g. adding children, adding active duty population, etc.), significant change in study design (i.e. would prompt additional scientific review) or a change that could potentially increase risks to subjects.

15. SERIOUS BREACHES

A “serious breach” is a breach of the protocol or of the conditions or principles of Good Clinical Practice which is likely to affect to a significant degree –

- (a) the safety or physical or mental integrity of the trial subjects; or

(b) the scientific value of the research.

In the event that a serious breach is suspected the Sponsor must be contacted within 1 working day. In collaboration with the research team the serious breach will be reviewed by the P.I. Sponsor and reported to the Mayo Clinic IRB within seven calendar days. In addition, the Funder will be notified as per their requirements and in the ways stated in prior sections (Section 10.2).

16. ETHICAL AND REGULATORY CONSIDERATIONS

16.1. Declaration of Helsinki

The Investigator will ensure that this study is conducted in accordance with the principles of the Declaration of Helsinki.

16.2. Guidelines for Good Clinical Practice

The Investigator will ensure that this study is conducted in accordance with relevant regulations and with Good Clinical Practice.

16.3. Approvals

Following Sponsor approval the protocol, informed consent form, participant information sheet will be submitted to an appropriate Research Ethics Committee (REC), and HRA (where required) and host institutions for written approval.

The Investigator will submit and, where necessary, obtain approval from the above parties for all substantial amendments to the original approved documents.

As per Funder requirements, a DoD Human Research Protection Official (DHRPO) must:

- 1) Review the research protocol for compliance with DoD Instruction (DoDI) 3216.02 "Protection of Human Subjects and Adherence to Ethical Standards in DoD-Supported Research," accept the Institutional Review Board (IRB) determination of level of risk, ensure that the study is compliant with applicable DoD regulatory requirements and approve the protocol prior to implementation.
- 2) Review and accept IRB-approved substantive changes to an approved research protocol before they are implemented.
- 3) Ensure the IRB conducts an appropriate continuing review at least annually.

16.4. Other Ethical Considerations

Not applicable.

16.5. Reporting

The PI shall submit once a year throughout the study, or on request, an Annual Progress report to the IRB and funder (where required). In addition, an End of Study notification and final report will be submitted to the same parties.

16.6. Participant Confidentiality

The study will comply with the Mayo Clinic regulations for protecting patient information, which require data to be de-identified as soon as it is practical to do so. The processing of the personal data of participants will be minimized by making use of a unique participant study number only on all study documents and any electronic database(s), with the exception of the CRF, where participant initials may be added. All documents will be stored securely and only accessible by study staff and authorized personnel. The study staff will safeguard the privacy of participants' personal data.

16.7. Expenses and Benefits

Reasonable travel expenses for any visits additional to normal care will be reimbursed on production of receipts, or a mileage allowance provided as appropriate.

17. FINANCE AND INSURANCE

17.1. Funding (see budget)

17.2. Insurance (Patient insurance as needed)

17.3. Contractual arrangements

Appropriate contractual arrangements will be put in place with all third parties. These include the HRA statement of activities and schedule of events, as well as all relevant DARPA documents.

18. PUBLICATION POLICY

The Investigators will be involved in reviewing drafts of the manuscripts, abstracts, press releases and any other publications arising from the study. Authors will acknowledge funding resources for this study. Authorship will be determined in accordance with the ICMJE guidelines and other contributors will be acknowledged.

19. DEVELOPMENT OF A NEW PRODUCT/ PROCESS OR THE GENERATION OF INTELLECTUAL PROPERTY

Ownership of IP generated by employees of Mayo Clinic is the property of Mayo Clinic.

20. ARCHIVING

Patient identifiable information will be stored in encrypted files on password-protected computers for 3 years after the study has finished. This excludes any research documents with personal information, such as consent forms, which will be held securely at Mayo Clinic for ten years after the end of the study - the period necessary for their full analysis and writing up of all scientific publications).

